- d. To compare the neonatal outcomes between membrane sweeping and transcervical Foley catheter for IOL in women with one previous Caesarean delivery.
 - i. APGAR score at 5 minutes.
 - ii. Cord pH.

- e. To compare women's evaluation on the care they receive between membrane sweeping and transcervical Foley catheter for IOL.

STATEMENT ON ETHICAL ISSUES

1. Institutional Review Board (IRB) Review:
 - a. The study protocol will be reviewed by Medical Research Ethics Committee (MREC) of Ministry of Health, Malaysia.
2. Patient information sheet and informed consent:
 - a. Written informed consent will be obtained from each subject prior to the enrollment.
 - b. Subjects will be told of the objective of this study in clear laymen's term. They will be informed of their rights as subjects and that their participation is voluntary.
 - c. Subjects will also be notified that if they choose to withdraw from the study at any time, they will be managed according to local protocol under Department O&G, Sibuh Hospital.
 - d. The information sheet specifies whom to contact if they are injured as a result of the study, and whom to contact with general information about the study.
 - e. The consent form specifies that the study staff, and governmental or regulatory authorities, have direct access to subject's medical record in order to make sure that the study is conducted correctly and the data are recorded correctly.
 - f. Compliance with informed consent will be monitored by the principal investigators.

TRIAL DESIGN

1. Study location:
 - a. This study will be conducted in the Department of Obstetrics and Gynaecology, Sibuh Hospital, Sarawak.

2. Study design:
 - a. A prospective randomised controlled trial (RCT) will be conducted.
 - b. The subjects will be followed-up from time of IOL till delivery.

3. Study endpoint:
 - a. The study endpoint is to confirm the superiority of membrane sweeping and transcervical Foley catheter for IOL in women with one previous Caesarean delivery.

4. Study duration:
 - a. This study will be conducted from 15 November 2017 till 24 September 2018.

5. Study procedure: (see flow chart in Appendix 1)
 - a. Approval will be obtained from the Medical Research & Ethics Committee, Ministry of Health Malaysia before conducting the study.
 - b. Pregnant women with one previous Caesarean section who are indicated for IOL and eligible will be recruited in the study.

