 - c. Informed consent available in either English or Malay language (See Appendix 2) will be obtained prior to enrollment into the study. The consent will be taken by the principal investigator at time of admission in Sibug Hospital Labour Ward.
 - d. A data collection form will be filled up and details including personal information will be obtained (Appendix 3).
 - e. Eligible subjects will be randomly assigned to one of the treatment groups below.
 - i. Group 1: IOL with membranes sweeping
 - ii. Group 2: IOL with transcervical Foley catheter
 - f. Blocked randomisation, in a block size of 6 and an allocation ratio of 1:1, will be performed using a computer-generated randomisation sequence by Research Randomizer (available online at <https://www.randomizer.org/>). The allocation assignment indicating “membrane sweeping” or “transcervical Foley catheter” will be sealed in sequentially numbered, opaque envelopes by principal investigator, . Envelopes will be kept in a locked box in Labour Ward. When study consent is signed, the next sequential envelope will be taken out from the box and opened to determine allocation.

- g. This is a non-blinded study in which subjects, medical staffs, and investigators are not blinded to group assignment. This is because both IOL methods are distinctly different procedure. However, both intervention arms are considered receiving equal treatment. In term of safety, both membrane sweeping and transcervical Foley catheter are non-pharmacological in nature and thus the risk of scar rupture does not differ in both methods. In term of efficacy, there is no previous study to compare effectiveness between these two methods. Individual studies revealed that membrane sweeping is likely to reduce the need for formal IOL in post-date pregnancy and transcervical Foley catheter could improve cervical favourability.
- h. IOL will be done on the next morning. Pre-induction cardiotocograph (CTG) will be performed to ensure normal fetal heart rate prior to IOL.
- i. In Group 1, membrane sweeping involves the insertion of a digit past the internal cervical os followed by three circumferential passes of the digit causing separation of the membranes from the lower uterine segment. When the cervix is closed, a massage of the cervical surface for 15 to 30 seconds will be performed instead. Membrane sweeping will be undertaken twice a day at 8 to 10 hours apart.

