Dilatation (cm)	1	1-2	3-4	>4
Length of cervix (cm)	>4	2-4	1-2	<1
Station	-3	-2	-1	0
Consistency	Firm	Average	Soft	-

Position	Posterior	Mid/Anterior	-	-
----------	-----------	--------------	---	---

SELECTION AND WITHDRAWAL OF SUBJECTS

1. Sample population:
 - a. All pregnant women with one previous Caesarean section who are admitted to Sibug Hospital for IOL will be recruited in the study.
2. Inclusion criteria:
 - a. The inclusion criteria are age at least 18 years old, gestational age ≥ 37 weeks, singleton pregnancy, reassuring fetal status and modified Bishop score ≤ 6 .
3. Exclusion criteria:
 - a. Women with ruptured membranes, intrauterine death, polyhydramnios, severe fetal anomalies, multiple pregnancy.
 - b. Women with contraindications for IOL eg. placenta previa, suspected macrosomia, suspected cephalopelvic disproportion, non-cephalic presentation, and obstructive pelvic masses.
4. Sample size determination:
 - a. We had searched electronic databases including PubMed, Cochrane Library, Scopus, Ovid, JSTOR and Google Scholar. We found that there was no study comparing the two IOL methods, thus no prior information is available for sample size calculation.
 - b. Based on Julious SA (32), we will recruit 24 subjects (a sample size of 12 per group) first, then do an interim analysis and calculate the actual sample size required for a full RCT. The justifications for this interim sample size are based on rationale about feasibility, precision about the mean and variance, and regulatory considerations.
 - c. With α at 0.05 and power at 0.8, the final sample size will be calculated based on the study primary outcome of induction to delivery interval. As this outcome is a continuous data, we will use the following formula by Snedecor and Cochran 1989 to calculate the sample size (including 15% of dropout rate).

$$n = 1 + 2C \left(\frac{s}{d} \right)^2$$

s = standard deviation,

d = the difference to be detected, and

C = constant

5. Consent taking:

- a. Pregnant women with one previous Caesarean section who are indicated for IOL and eligible will be recruited in the study.
- b. Participation of the subjects is voluntary and will not affect medical services.
- c. Informed consent available in either English or Malay language (See Appendix 2) will be obtained prior to enrollment into the study.
- d. The consent will be taken by the principal investigator at time of admission in Sibu Hospital Labour Ward.

6. Subject withdrawal:

- a. Criteria:

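### A single fixed block of 6 in this open-label, one-hospital trial lets an enroller who keeps count know on average one allocation in four in advance

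*Combined protocol and SAP*

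**What the plan says.** Study procedure, item f, sets out "Blocked randomisation, in a block size of 6 and an allocation ratio of 1:1" from a web-based generator. The assignments "will be sealed in sequentially numbered, opaque envelopes by principal investigator" and are kept in a locked box in the Labour Ward. Once consent is signed, "the next sequential envelope will be taken out from the box and opened to determine allocation".

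Item g of the same section states: "This is a non-blinded study in which subjects, medical staffs, and investigators are not blinded to group assignment". Items c (Study procedure) and 5d (Selection and Withdrawal of Subjects) give enrolment to the role that seals the envelopes: "The consent will be taken by the principal investigator at time of admission in Sibu Hospital Labour Ward".

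Trial Design, item 1, names a single hospital department. No stratification is described, so there is one running list. The only sample size stated is the first 24 women, 12 per group (Sample size determination, b), which is four complete blocks of 6. Nothing in the protocol varies the block size or withholds it from the people who enrol.

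**The concern.** Concealment means that whoever decides whether and when to offer enrolment cannot foresee the next assignment. Numbered opaque envelopes protect against looking inside the next one. They do not protect against deduction from those already opened. With every block the same size and past assignments not blinded, the rest of a block is known as soon as one arm has taken its three places.

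Some discretion exists before consent: whom to approach, in what order, and whether to offer the trial. Eligibility admits any modified Bishop score of 6 or less, so the state of the cervix varies among eligible women and can be seen before enrolment. The protocol also links the cervix to the route to delivery: at 24 hours a favourable cervix leads to amniotomy, and an unfavourable one to a further day. The primary outcome is the overall induction to delivery interval, compared by t-test or Mann-Whitney test without baseline adjustment (Statistics, item 2). If foreknowledge influenced who entered which arm, those tests would carry the imbalance into the result. The first 24 women also determine the final sample size, so distortion there would reach the planning of the rest of the trial.

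**Working it through.** The documents give no predictability figure, so there is none to reproduce.

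**Inputs.** Block size 6 and ratio 1:1, hence 3 + 3 per block (item f). One site and no stratification, hence one list. Past assignments unblinded (item g). Envelopes used in strict order (item f). First look at 24 women = 4 blocks.

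**Allocations known with certainty.** There are C(6,3) = 20 equally likely blocks. An allocation is certain once one arm has used its three places.
- 4th place: certain if the first three are all in one arm: 2/20 = 10%.
- 5th place: certain if the first four split 3 to 1: 8/20 = 40%.
- 6th place: always certain, 100%.

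Expected number per block = 0.10 + 0.40 + 1.00 = 1.5, and 1.5/6 = 25%. The general formula for a block of 2m is 2m/(m + 1); with m = 3 this is 6/4 = 1.5. Over the first 24 women, 4 × 1.5 = 6 certain allocations are expected, and at least 4 (one per block) are guaranteed.

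**Correct guesses.** The strategy is to guess the arm with more places left and toss a coin when they are level. The chances of being right by place are 0.5, 0.6, 0.6, 0.7, 0.7 and 1.0. The sum is 4.1, and 4.1/6 = 68.3%, against 50% with no information.

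**Other fixed sizes.** The certain share, 1/(m + 1), is 1/3 for blocks of 4, 1/5 for blocks of 8 and 1/6 for blocks of 10. A different fixed size does not solve the problem.

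**Varying sizes.** These figures are simulated. The guesser knows the set of sizes but not their order, tracks every allocation, and updates exactly.

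| Design | Certain in advance | Best guess correct |
|---|---|---|
| Fixed 6 | 25% | 68% |
| 4, 6, 8 drawn freely | about 2% (2.2% to 2.5% for lists of 24, 72 or 120) | about 68% |
| First 24 built from 4, 6, 6, 8 in random order | about 9% | about 68% |

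In numbers per 24 women, that is 6 certain allocations under the fixed block, about 0.02 × 24 ≈ 0.5 with free drawing, and about 0.09 × 24 ≈ 2.2 with the constrained set. The constrained set does worse because a guesser who knows it also knows that it closes at 24: the 24th allocation is then always known, and the 23rd in about 39% of lists.

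**The case against.** **Limited room to act.** Consent is taken at admission for an indicated induction that follows the next morning, the stated population is all eligible admissions, and entry is capped at a Bishop score of 6. This narrows the scope for steering. It does not remove it, because the order of approach and the decision not to offer consent remain. Baseline Bishop score, parity and scar history are tabulated by arm in the dummy tables, so gross selection on them could be seen, but the planned tests would not correct it.

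**No stated preference.** The protocol regards the two arms as equal treatment, and nothing in it shows that anyone favours one. This stands. A reader might infer that the trial's result is biased, or that the primary outcome is known to depend strongly on features seen at enrolment. The documents support neither: they contain no figure for that dependence and no sign that selection took place.

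**The condition on the 25%.** It is a long-run average over complete blocks and needs someone who knows the block size and keeps count. It would be too much to say that everyone sees each allocation, since item g says only that groups are unblinded. The principal investigator, however, is placed to meet both conditions.

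**Envelope preparation is the larger weakness.** This also stands. The role that seals the envelopes takes consent and could in principle know the whole list. A reader might infer that varying the blocks alone would restore concealment. It would hide nothing from that person. The two weaknesses are still distinct: with fully independent preparation, a fixed block of 6 would leave 25% certain.

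**Most predictability remains.** The best-guess rate stays near 68% with varied blocks. The gain is the removal of most of the certainty, not of guessing.

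**Conclusion.** The point holds as an avoidable exposure to selection bias. Under the plan as written, 25% of allocations are certain in advance and 68% can be guessed by an enroller who knows the block size and counts. For the first 24 women that is 6 expected certain allocations, and never fewer than 4. These figures are exact for complete blocks of 3 + 3 on one list; an incomplete final block would lower the share slightly.

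The size of any bias in hours of induction to delivery cannot be derived from the documents. The figure of about 2% after the change assumes freely drawn sizes and a guesser who does not know their order. It should not be carried over to a first 24 forced to 12 per group, where about 9% remains certain to someone who knows the set. It also depends on keeping the list from the person who enrols. On that footing the change is a cheap and worthwhile improvement, not the repair of a demonstrated bias.

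**What to change.** 1. Replace the fixed block in item f with permuted blocks of 4, 6 and 8, the size of each drawn freely at random.
2. Have an existing staff member who does not take consent generate the list and seal the envelopes. Without this step, the first has no effect on the principal investigator's knowledge.
3. Keep the block sizes out of the documents held by enrolling and ward staff, state there only that sizes vary, and report the sizes at the end.
4. Prefer free drawing to a first 24 forced to exactly 12 per group. If exact balance at the first look is wanted, blocks of 4, 6, 6 and 8 in random order provide it, at about 9% certain instead of about 2%.

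**Cost.** A new list, a sentence or two of protocol text, and one reassigned task. If recruitment or the interim look falls inside a block, the arms can differ by up to 4 (half of 8) instead of up to 3 (half of 6). If enrolment has already begun, apply the change to the unopened envelopes and report the fixed block used until then as a limitation.

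### The role that seals the allocation envelopes is also the role that takes consent, with no stated separation of people, so concealment from the enroller is not assured

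*Combined protocol and SAP*

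**What the plan says.** Trial Design, section 5 (Study procedure), item f describes the randomisation: "Blocked randomisation, in a block size of 6 and an allocation ratio of 1:1, will be performed using a computer-generated randomisation sequence", made with an online tool. The assignments "will be sealed in sequentially numbered, opaque envelopes by principal investigator", and the envelopes go into a locked box in the Labour Ward. Then: "When study consent is signed, the next sequential envelope will be taken out from the box and opened to determine allocation".

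Item c of the same section says: "The consent will be taken by the principal investigator at time of admission in Sibug Hospital Labour Ward". Selection and Withdrawal of Subjects, item 5.d, repeats this. Item 5.g makes the trial open to women, staff and investigators.

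The visible text does not say who generates or holds the sequence, who has the key to the box, or who opens the envelope. It does not bar the person who seals from enrolling.

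Three features of this copy limit what can be concluded:

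- The wording in 5.f, "opaque envelopes by principal investigator, . Envelopes will be kept in a locked box in Labour Ward", has a gap where a name appears to have been removed.
- The ethics statement, item 2.f, uses the plural: "Compliance with informed consent will be monitored by the principal investigators".
- The Appendix 1 flow chart is not shown.

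**The concern.** Concealment requires that whoever decides to approach and enrol a woman cannot know her allocation beforehand. The plan's safeguards achieve this for staff who did not prepare the envelopes. They do nothing against a person who put the assignments in and then recruits, and the text gives both tasks to one role.

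There is room for such knowledge to act. The plan intends to recruit every eligible woman admitted for induction. But eligibility includes matters of judgement settled before consent: a modified Bishop score of 6 or less, suspected macrosomia and suspected cephalopelvic disproportion. The consent discussion can also be influenced, even unintentionally.

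The primary outcome, overall induction to delivery interval, is compared by an unadjusted t-test or Mann-Whitney test (Statistics, item 2). Dummy Tables 1 and 2 might reveal some imbalance, but nothing in the analysis would correct it. This is an exposure in the design, not evidence of misuse.

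**Working it through.** **Text check.** The plan gives no figure on this point, so the first check sets the statements on each task side by side.

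| Task | Who, in the visible text | Where |
|---|---|---|
| Generate the sequence | Not stated (online tool) | Trial Design 5.f |
| Seal the envelopes | Principal investigator (name apparently removed) | Trial Design 5.f |
| Hold the list or the key | Not stated | – |
| Take consent | Principal investigator | Trial Design 5.c; Selection 5.d |
| Open the envelope | Not stated | Trial Design 5.f |

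Sealing and consent fall to one role, and no statement separates the people.

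**Illustration 1: the enroller knows the sequence.** The documents give no SD and no final sample size. Only the 24 women of the interim stage (Selection 4.b) are stated. The totals of 60 and 126 and the shift *d* are assumptions. If knowledge of the allocation raises the mean prognosis by *d* SD in one arm and lowers it by *d* in the other, then:

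- false difference = 2*d* SD
- noncentrality = 2*d* × √(N/4), with N − 2 degrees of freedom
- type I error = probability that |t| exceeds the two-sided 5% critical value.

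For *d* = 0.10 and N = 24, the noncentrality is 0.20 × √6 = 0.49 and the critical value is 2.07 (22 degrees of freedom). The result is 7.6%.

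| Shift *d* | False difference | N = 24 | N = 60 | N = 126 |
|---|---|---|---|---|
| 0.05 SD | 0.10 SD | 5.6% | 6.7% | 8.6% |
| 0.10 SD | 0.20 SD | 7.6% | 11.9% | 20.0% |
| 0.15 SD | 0.30 SD | 10.8% | 20.8% | 38.6% |

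Simulation of 100,000 trials at *d* = 0.10 gave 7.5%, 11.8% and 19.8%.

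**Illustration 2: roles separated, enroller only counts blocks.** This is a separate and secondary matter. All 20 possible orders of a 1:1 block of 6 were enumerated. On average 1.5 of 6 allocations (25%) are certain from earlier ones, and the best guess is right for 4.1 of 6 (68.3%). Separating the roles does not change these figures. If the enroller acts on every guess:

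- false difference = 2*d* × (2 × 0.6833 − 1) = 0.3667 × 2*d*.

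| Shift *d* | False difference | N = 24 | N = 60 | N = 126 |
|---|---|---|---|---|
| 0.05 SD | 0.037 SD | 5.1% | 5.2% | 5.5% |
| 0.10 SD | 0.073 SD | 5.3% | 5.9% | 6.9% |
| 0.15 SD | 0.110 SD | 5.8% | 7.0% | 9.4% |

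Simulation at *d* = 0.10 gave 5.1%, 5.8% and 6.7%.

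**The case against.** The strongest objection is that this copy cannot settle who does what. The removed name sits exactly where the plan identified the sealer, and item 2.f of the ethics statement allows more than one principal investigator. The separation may already exist. This stands, and it is why the conclusion stops at concealment not being assured. A name alone would not close the gap, however: the plan would still have to say that this person does not recruit or take consent.

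Second, the path to bias has links the documents leave open. They do not say that the consent-taker also scores the cervix or judges suspected macrosomia or disproportion, and some of that may be decided before consent. Sealing envelopes does not in itself mean keeping or remembering the list. Both points are fair. They lower the likelihood of harm but do not supply the missing safeguard.

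Third, the illustration assumes full knowledge of the sequence and opposite shifts in the two arms, which is close to a worst case. The largest figures occur only at an assumed total of 126. That is correct: the point rests on the text, and the figures show only what could be at stake.

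Finally, no passage mentions a research office or an uninvolved colleague in this self-funded, single-department study. That the fix is cheap is therefore a reasonable expectation rather than something the documents establish.

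**Conclusion.** The concern holds, with moderate confidence. On the visible text one role seals the envelopes and enrols the women, and the remaining safeguards do not protect against that combination. The limit is the possibility that two people share the role.

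The amount of bias is unknown. Under the assumed 0.1 SD shift with a known sequence, the nominal 5% error would be about 8% at 24 women, 12% at 60 and 20% at 126. With roles separated and block counting alone, the same shift gives about 5%, 6% and 7%. Role separation would therefore remove most of the exposure, but not all of it, if the enroller did know the sequence. The plan should make the change because internal validity is at stake and the remedy is small.

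**What to change.** Amend Trial Design 5.f as follows:

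- An existing department or research-office colleague who neither recruits, consents nor induces women generates the sequence, seals the envelopes and holds the list away from the Labour Ward.
- The plan states who opens the envelope.
- The woman's study ID, the date and the time are written on the envelope before it is opened. This leaves a record of the sequence, which is useful because withdrawn women's data are to be destroyed and the women replaced (Selection 6.b and 6.c).

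If the name removed in 5.f already belongs to such a person, one sentence saying so is enough.

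The cost is a small clerical task. It is repeated if the sequence is extended after the interim at 24 or for replacements. No visits or assessments are added, and keeping blocks of 6 preserves 12:12 among the first 24 allocated.

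Undisclosed varied blocks (for example 4, 6 and 8) are optional and not part of this fix. They would cut certain allocations from 25% to about 2%, but guess accuracy would stay at about 67 to 68% and the type I error from counting would be almost unchanged. With the three sizes equally likely, the arms would be unequal at 24 in 27.5% of sequences (by 2 women in 27.2%, by 4 in 0.3%).

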 - i. Subjects may withdraw voluntarily from study at any time upon their request.
 - ii. Subjects are inappropriately enrolled without fulfilling inclusion/exclusion criteria.
 - iii. Subjects develop spontaneous labour before IOL procedure is undertaken.
- b. Follow up process:
 - i. The withdrawn subjects will be managed according to local protocol under Department O&G, Sibu Hospital.
 - ii. The withdrawn subjects data will be destroyed as it will not be used for data analysis.
- c. The withdrawn subjects will be replaced with new subjects in order to meet the required sample size.

TREATMENT AND PROCEDURES

1. Treatment and medications that are permitted during the trial:
 - a. Amniotomy
 - b. Oxytocin augmentation when contractions are not optimised
 - c. Abdominal and vaginal examination to assess labour progress
 - d. Intrapartum continuous fetal heart rate monitoring
 - e. Fetal scalp sampling in the presence of non-reassuring fetal heart rate
 - f. Instrumental delivery or emergency Caesarean section if indicated

2. Both IOL methods of membrane sweeping and transcervical Foley catheter do not contain drug or medication. Thus, the risk of uterine rupture is similar to spontaneous labour in women with previous Caesarean delivery. If scar dehiscence is highly suspected during labour, standard management with recourse to emergency Caesarean section will be undertaken.

3. Treatment and medications that are not permitted during the trial:
 - a. Vaginal prostaglandin E2

ASSESSMENT OF EFFICACY

1. Primary outcome:
 - a. Overall induction to delivery interval.
2. Secondary outcomes:
 - a. Induction outcomes:
 - i. Improvement of modified Bishop score at interval of 24 hours and 48 hours after induction.
 - ii. Whether oxytocin augmentation is required.
 - b. Delivery outcomes:
 - i. Mode of delivery.
 - ii. Duration of oxytocin augmentation overall and in vaginal delivery group.
 - iii. Induction to vaginal delivery interval.

- iv. Amniotomy to vaginal delivery interval.
- v. Vaginal delivery rate within 24 hours of induction and between 24-48 hours of induction.
- c. Maternal outcomes:
 - vi. Uterine hyperstimulation (> 5 contractions per 10 minutes for at least 20 minutes or a contraction lasting at least 2 minutes with/without abnormal fetal heart rate).
 - vii. Uterine rupture.
 - viii. Post-partum haemorrhage (estimated blood loss \geq 500 ml).
 - ix. Maternal pyrexia (temperature >38.0 °C once, or 37.5 °C on two occasions 2 hours apart).

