32. Julious SA. Sample size of 12 per group rule of thumb for a pilot study. *Pharm Stat*. 2005;4(4):287-91.

Appendix 1

Study Procedure Flow Chart

Appendix 3

DEPARTMENT OF O&G, SIBU HOSPITAL, SARAWAK

DATA COLLECTION FORM

**MEMBRANE SWEEPING VERSUS TRANSCERVICAL FOLEY CATHETER
FOR INDUCTION OF LABOUR IN WOMEN WITH PREVIOUS
CAESAREAN DELIVERY**

Patient ID :

Name : **Date/time of admission:**

IC Number : **Date/time of discharge :**

MRN :

Age :

Ethnicity : Iban Melanau Bidayuh Malay
 Chinese Indian Other Foreigner

ALLOCATED GROUP: (PLEASE TICK)

MEMBRANE SWEEPING

TRANSCERVICAL FOLEY CATHETER

SECTION A: DEMOGRAPHIC INFORMATION

Gravida / Parity:/..... Gestational age at induction of labour: weeks days

EDD/REDD:

Height (m):

Weight (kg): (at booking) (at delivery)

BMI (kg/m²):

Previous Caesarean section: *(please tick)*

a) Untested scar

If untested scar, any previous vaginal delivery?

Yes

No

b) Tested scar

Indication of induction of labour: *(please tick)*

a) Postdate

b) Fetal growth restriction

c) Hypertension

d) Diabetes

e) Other

Please specify:

SECTION B: INDUCTION OUTCOMES ***Modified Bishop score is used in this study*

Modified Bishop score:

a) At the start of induction

b) When Foley catheter dislodged < 24 hours

a) After 24 hours of induction

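### The envelope is opened at admission although induction is the next morning, so baseline Bishop scoring and any pre-treatment exit from the trial happen with the arm known

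*Combined protocol and SAP*

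**What the plan says.** Trial Design, section 5 (Study procedure), sets the order of steps.

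- **Consent (5.c):** "The consent will be taken by the principal investigator at time of admission in Sibug Hospital Labour Ward".
- **Assignment (5.e):** "Eligible subjects will be randomly assigned to one of the treatment groups below".
- **Disclosure of the arm (5.f):** "When study consent is signed, the next sequential envelope will be taken out from the box and opened to determine allocation".
- **Blinding (5.g):** none, for women, staff or investigators.
- **Induction (5.h):** "IOL will be done on the next morning. Pre-induction cardiotocograph (CTG) will be performed to ensure normal fetal heart rate prior to IOL".

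The inclusion criteria (Selection and Withdrawal of Subjects, section 2) include "reassuring fetal status and modified Bishop score ≤ 6". No assessment time is given for either item.

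In Appendix 3, Section B, the only Bishop score before treatment is labelled "a) At the start of induction". Dummy Table 2 reports that score, the scores at 24 and 48 hours, and the change.

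Selection and Withdrawal of Subjects, 6.a, gives three reasons for withdrawal: the woman's own request at any time, enrolment that did not meet the criteria, and "Subjects develop spontaneous labour before IOL procedure is undertaken". Under 6.b and 6.c the data of withdrawn women are destroyed and new women replace them.

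**The concern.** Randomisation makes the arms comparable at the moment of allocation. Anything between allocation and the start of treatment that can depend on knowledge of the arm may undo this. Here that gap is a whole night, in a trial where everyone knows the arm.

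Two things are at stake. First, a woman may withdraw because of the arm she drew, or staff may judge her eligibility or onset of labour differently by arm. She then disappears from the data, so any imbalance cannot be examined later. Second, the Bishop score is a judgement made at internal examination. If the baseline is scored with the arm known, any tendency to score one arm lower or higher enters the comparison of change in score. Nothing in 5.h to 5.j requires the arm to be known before the morning.

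**Working it through.** The point rests on the order of steps. The plan gives no final sample size, standard deviation, target difference or rate of women who never start, so there is no figure of its own to reproduce.

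**Step 1. The order.**

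| Step | When | Arm known? | Source |
|---|---|---|---|
| Consent | Admission | No | 5.c |
| Envelope opened | On signature of consent | From here on, yes | 5.f |
| Overnight wait | Admission to next morning | Yes | 5.h |
| Pre-induction CTG | Before induction | Yes | 5.h |
| Baseline Bishop score | Start of induction | Yes | Appendix 3, Section B |
| Sweep or catheter | Next morning | Yes | 5.h to 5.j |

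Item 5.d (filling in the form) is listed before 5.e and 5.f, but the label of the Bishop field places that score at the start of induction, after disclosure.

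**Step 2. Baseline score.** Change = later score − baseline score. If knowing the arm moves the mean baseline in one arm by δ, the between-arm difference in mean change moves by −δ. The documents give no basis for a value or sign of δ. The raw 24-hour and 48-hour scores are not affected by it.

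**Step 3. Eligibility.** Items 5.b and 5.e describe women as eligible before assignment. No item says when fetal status or the Bishop score is checked for that purpose, and the form has no field for a check before allocation. Rule 6.a.ii has no time limit, so eligibility can be looked at again once the arm is known.

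**Step 4. Exits before treatment.** All three reasons in 6.a can operate overnight. Labour that starts before either procedure cannot be caused by the procedure, so it should be balanced between arms in expectation. A decision to withdraw, or a judgement about eligibility or labour onset, has no such protection.

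Changing the analysis rule alone would not cure this. The primary outcome is the interval from induction to delivery, and a woman who labours before induction has no start time for it.

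**Step 5. Scale, on assumed rates only.** Let f be the share of allocated women removed before treatment. Among the first 24 women (Selection and Withdrawal of Subjects, 4.b), the expected number removed is 24f, and the chance of at least one is 1 − (1 − f)^24. As an outer bound for bias, suppose the slowest share q of one arm only were removed and the interval were normally distributed. With c the standard normal quantile at 1 − q and φ the normal density, that arm's mean falls by φ(c)/(1 − q) standard deviations.

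| Assumed f or q | Expected removals of 24 | Chance of at least one | Outer-bound shift (SD) |
|---|---|---|---|
| 2% | 0.5 | 38% | 0.05 |
| 5% | 1.2 | 71% | 0.11 |
| 10% | 2.4 | 92% | 0.19 |
| 15% | 3.6 | 98% | 0.27 |

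The last column is a ceiling, not an estimate. Removal before treatment can select only through prognosis, since the interval itself is not yet known. Removal unrelated to arm and outcome gives no expected shift.

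**The case against.** The strongest reply is that the protocol already puts eligibility first: eligible women are recruited (5.b) and eligible women are assigned (5.e). That stands. A reader might infer from 5.h that the morning CTG is the eligibility test, so that eligibility is settled with the arm known. The documents do not support this. The CTG is described only as a safeguard before induction, no rule in 6.a names it, and nothing says the Bishop criterion is tested again in the morning. What remains is that the check before allocation is neither timed nor recorded, and that 6.a.ii can be applied late.

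A reader might also infer that women who labour overnight dilute the treatment difference in proportion to their number. That would describe an analysis the plan does not make: these women are withdrawn and not analysed.

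Third, change in Bishop score is one of several secondary outcomes, and the later scores are also given with the arm known. Both facts stand. Recording the baseline before allocation protects the baseline only, and does not make the measurement of change blind.

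Fourth, the larger harm comes from destroying and replacing withdrawn women's data. That is a fair ranking, but it is a separate defect. Early disclosure is what creates many of the opportunities for it to operate.

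**Conclusion.** The point holds as a weakness in the order of steps that should be corrected. The arm is disclosed a night earlier than the procedures require. As a result, the form's only pre-treatment Bishop score is taken with the arm known, and women can leave the trial after allocation and before treatment without trace.

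It does not show that eligibility is decided after allocation, that overnight labour by itself biases the comparison, or that the primary outcome is distorted by a known amount. The bias could run in either direction, and its size cannot be derived from the documents; the table above is illustration on assumed rates.

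The conclusion assumes that practice follows 5.c to 5.h as written and that the form's label states when the baseline score is taken. The Appendix 1 flow chart is not visible in the text reviewed. If it shows a recorded assessment before allocation, the part about eligibility checks weakens; the early disclosure in 5.f and the labelled timing of the baseline remain.

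**What to change.** Keep consent at admission. Amend 5.f, with 5.e, 5.h and the flow chart to match, so that the envelope is opened the next morning, immediately before the procedure, and only after three items are recorded on the form:

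1. the result of the pre-induction CTG;
2. the baseline modified Bishop score, still meeting the protocol's own inclusion criterion;
3. the absence of labour.

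A consented woman who does not pass these checks is counted as a screen failure and uses no envelope. Adjust 6.a accordingly: the reason concerning spontaneous labour before the procedure would then rarely apply after allocation. The clinical care of women who are not randomised is unaffected.

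The cost is small: a few sentences, space on the form for the three entries, and no additional test or visit. The arm is known some hours later, so the procedure cannot be prepared the evening before. Someone must also be available to open the envelope in the morning; the documents do not say who that would be, so the amendment should name the role. The handling of women who still leave after allocation (6.b and 6.c) needs its own correction, which this change makes less consequential but does not replace.
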